## 6.0 Study Design and Procedures

All human subjects research will be conducted at the Institute for Health Research and Policy at UIC. Some portions of the data analyses conducted by Co-I [name] may take place at the University of Chicago. [name] role involves guiding the data analyses and writing up results for presentation and publication. [name] will only have access to a deidentified dataset and will not have any responsibility for recruitment, enrollment, consent, or data collection, and will never be able to access any participant contact information.

**Design Overview.** Participants will complete baseline assessments and a one-week EMA wave while they continue their usual pattern of cigarette use. After their first EMA week, participants will be randomized (within sex) in a 1:1 ratio to receive either SREC pods in their usual flavor (n=60) or pods in their choice of flavor (n=60). Participants assigned to the flavor choice condition can select from the four available SREC flavors (tobacco, menthol, watermelon, and blueberry) based on their preference and satisfaction with the flavor throughout the trial. All participants will receive brief behavioral counseling about reducing their cigarette use and switching to the SREC. After an initial week of using SREC and reducing the number of cigarettes smoked, participants will complete another EMA week assessing patterns and responses to use of both products. Participants will receive 12 weeks of SREC pods; complete daily reports of product use along with bi-weekly check-ins through the end of the 12-week trial, and then complete a one-month follow-up. Female participants of childbearing age (55 years old and younger) will provide urine for a required pregnancy test every 5 to 6 weeks and will be removed from the study if the test indicates a pregnancy. The total study duration for participants is 18 weeks. Table 1 shows the timeline of assessments, procedures, and modality.

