**Table 1: Timeline of Assessments and Procedures**

Week	Procedures	Modality	Visit Duration (in minutes)
0	Screening eligibility	On-line and phone	
1	CO; pregnancy test; baseline questionnaires on tablet (if not already completed); vital signs; height and weight; EMA training; go home with EMA and smoke usual cigarettes	In-person visit	90-120
2	De-brief EMA; CO; Counseling about reduction and switch; brief questionnaire; given week supply of SREC; daily reports of use	In-person visit; daily text/web reports of use	60
3	Return used pods; CO; Brief counseling to problem solve reduction and switch; given new week supply of SREC; start EMA	In-person visit; daily text/web reports	40
4	Debrief EMA week; return used pods; CO; brief review of progress and problem-solve; given 2-week supply of SREC	In-person visit; daily text/web reports of use	40
5	Daily reports of use via text/web	Daily Text/web reports of use	
6	Brief check-in to give next 2-week supply of SREC; return used pods; CO; continue daily reports of use via text/web; pregnancy test	In-person visit; daily text/web reports of use	20
7	Daily reports of use via text/web	Daily Text/web reports of use	
8	Brief check-in to return used pods; given next 2-week SREC supply; CO; continue daily reports of use via text/web	In-person visit; daily text/web reports of use	20
9	Daily reports of use via text/web	Daily Text/web reports of use	
10	Daily reports of use via text/web	Daily text/web reports of use	
11	Brief check-in to return used pods; CO; given next supply of SREC; continue daily reports of use via text/web; pregnancy test	In-person visit; daily Text/web reports of use	20
12	Daily reports of use via text/web	Daily text/web reports of use	
13	Daily reports of use via text/web	Daily Text/web reports of use	
14	End-of-treatment full assessment battery; CO; vitals; height and weight; collect SREC device and remaining pods; daily reports of use surveys end	In-person	60
18	Brief follow-up about cigarette and ENDS use over past month	Web/phone based	15

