**Week 3 Visit.** Participants will bring back all used and unused pods for adherence counts, complete a brief questionnaire about subjective reactions and potential adverse effects from SREC, and complete the CO assessment. Study staff review their progress with reducing their smoking and switching to SREC and continue brief behavioral counseling about reducing smoking and substituting SREC. Participants will be told that their goal is to completely switch. Participants will receive feedback on their compliance with the first EMA week and additional training to ensure accurate reporting of both SREC and cigarettes on the app. Participants go home with another week supply of SREC, begin the second 7-day EMA wave, and continue completing daily reports.

**Week 4 Visit.** Similar to the week 3 visit, except that participants will again debrief their EMA week for compliance and problems; complete assessments; and review their progress with switching to SREC. Participants will receive a 2-week supply of SREC and continue completing daily reports.

**Weeks 5-13.** Participants will return to the study office every 2 to 3 weeks to return pods, receive a new supply, and complete CO assessments. During the week, they will continue completing daily reports. Additionally, female participants of childbearing age will provide a urine sample every 5 to 6 weeks; those with positive test results (a result indicating pregnancy) will be removed from the study.

**Week 14 (End-of-Treatment).** Participants return to the study office to complete a full assessment battery and return the SREC device and all pods. They will be encouraged to continue to stay off/reduce all combustible cigarettes but will not receive any more study provided SREC pods.

**Week 18 (One Month Follow-up).** Participants will receive an email or text prompt to complete a brief web-based survey (phone if needed) about their cigarette and ENDS use during the past month as well as motivation and confidence to continue to stay off combustible/use ENDS in the future.

All study procedures are being done for research purposes; none are part of their health services or care.

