Adverse Events (e.g., throat irritation, nausea)			x	X	x	x	x	x	x	x	x	x	x	x		

A. A **Comprehensive questionnaire** (baseline and 14-Week End of Treatment visits) will be completed in-person to assess key constructs [e.g., sociodemographics, tobacco and nicotine use (history, dependence, attitudes, motivations, intentions, perceived harm), tobacco environment, cessation history and intentions, and other substance use]. Each questionnaire will take approximately 30 - 40 minutes to complete. Shorter **brief surveys** (5-7 minutes to complete) will be completed at weeks 2, 3, 4, 6, 8, and 11. These measures serve as important descriptors of our sample, serve as covariates or moderators in our analyses, and serve as predictors of success in reducing cigarettes and switching to SREC over time.

B. A **daily use survey** completed online via REDCap from an emailed or texted survey link starting at the week 2 visit through the week 14 visit (over the 12 treatment weeks) to assess the use of cigarettes, SREC, and any other e-cigarette/nicotine vaporizer. Each of these surveys will take about 1 minute to complete. This brief survey will serve as an indicator of change in patterns of use as well as a way for the Clinical Interviewer Staff to track progress with cigarette reduction and to monitor nicotine exposure during the treatment phase. Daily surveys ask about the number of cigarettes smoked and the number of SREC or other e-cigarette episodes on the previous day (an episode is defined as 15 puffs or a period lasting about 10 mins). We also ask if the participant finished a pod on the previous day.

C. **Two, week-long waves of EMA data collection** using a **study provided smartphone**, the first wave will take place immediately following completion of the baseline questionnaire (week 1 visit through week 2 visit), and the second wave will take place starting at the week 3 visit through the week 4 visit. The first week of EMA provides the baseline comparison with combustible cigarettes to the second EMA wave when participants will have one week of experience with using the SREC and some practice cutting down on their cigarette smoking. Each EMA wave will cover 7 consecutive days, ensuring both weekday and weekend sampling.

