## **11.0 Data and Safety Monitoring**

This trial will be monitored by [name]. (PI), [name]. (Co-I), [name] (Data Manager), and an independent Data Safety Monitoring Board (DSMB) that will be chaired by a medical safety monitor: [name], MPH, FAAP, Professor of Pediatrics, College of Medicine, UIC. The DSMB will meet at the start of the trial to review the study protocol, safety and ethical issues, and to approve plans for data integrity. [name], [name], and [name] will meet weekly during the data collection phase to review and monitor the following items: participant accrual, participant complaints, participant drop-out, reasons for drop-out, adverse events, and any other problems related to study participation. Data accuracy and completeness will also be monitored weekly. During active recruitment, the DSMB will join these data review meetings quarterly to monitor participant safety.

The data report will be updated on a weekly basis and will include: participant accrual, participant complaints, participant drop-out, reasons for drop-out, adverse events, and any other problems related to study participation. The report will also include preliminary data on cigarette and SREC usage on a participant basis.

An AE is defined as any untoward medical or psychological event experienced by a patient during or as a result of his/her participation in the study that represents a new symptom or an exacerbation of an existing condition whether or not considered study-related based on appropriate medical judgment. SAEs are any adverse experience that results in any of the following outcomes: death, life-threatening event/illness, inpatient hospitalization or prolongation of existing hospitalization, persistent or significant disability/incapacity, pregnancy resulting in a congenital anomaly/birth defect, or any event requiring medical or surgical intervention to prevent permanent impairment or damage. In this study, this is defined as physician confirmed diagnosis of any of the following: angina pectoris, heart attack, stroke, transient ischemic attack, heart failure, coronary angioplasty or bypass surgery, peripheral vascular disease, and cancer (except for non-melanoma skin cancer). Non-SAEs are all adverse events that do not meet the above criteria for "serious."

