AEs will be systematically identified by querying participants at each of the in-person data collection time points after the start of treatment (week 2) through end of treatment (i.e., at weeks 3, 4, 6, 8, 11, and 14) using a standardized AE Patient Query Form to be adapted from [name] prior research studies using NRT while reducing cigarettes. AEs discovered outside of those planned evaluations, such as through other administrative interactions between research staff and participants (e.g., appointment reminder or rescheduling calls), will also be documented using the standardized AE form and followed up with to assure participant safety. Research staff will complete the AE forms directly into a centralized REDCap database in these circumstances. [name] will receive an automatic notification from REDCap upon submission of every AE report in order to trigger a review. The study safety monitor ([name]) will review, adjudicate, and document decisions or request that additional details be gathered from the participant, all

within the secure UIC REDCap web portal. Using this system, real-time AE reports can be generated at any time for the DSMB, UIC IRB, and/or NIDA, for both regularly scheduled reviews as well as in the event of any SAEs requiring expedited reviews.

**Expedited reporting.** All unexpected SAEs will be reported to the DSMB within 5 business days of discovery, regardless of any judgment of their relatedness to the study treatment. This reporting timeframe is consistent with the UIC IRB's requirements as described below. All relevant information will be reported to the DSMB for each unexpected AE including information about the event and its outcome, dosing history of a suspect medication/treatment, concomitant medications, the participant's medical history and current conditions, and all relevant laboratory data. An initial notification with all related study forms shall be made to the DSMB within 72 hours of the detection of an unexpected SAE. Any additional information about the case that may be obtained after the initial notification shall be communicated to the DSMB in a timely manner. The DSMB may require a conference call to review all the relevant information and the study safety monitor's determination of whether there was any possible relevance to the study and discuss and approve a Corrective and Preventive Action Plan, if warranted.

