We will discuss potential risks with participants at study enrollment and consent. We will discuss with participants that all tobacco use may present some harm, and that no tobacco use is healthy. We will also provide education to participants on the symptoms of nicotine toxicity (nausea and vomiting) so that they are aware and can reduce their exposure if they experience these symptoms. We also will provide participants with education on the recent outbreak of EVALI cases and how to identify if they may be experiencing the early signs and symptoms of an EVALI. At the enrollment visit (during the consent process) and at the end-of-treatment visit, we will tell participants that the long-term safety and health effects of using e-cigarettes is unknown. We will also discuss in-person and include on the information sheet that the SREC device may contain nicotine which can be hazardous to children and pets if ingested, in addition to informing the risk of nicotine use for pregnant and/or nursing women. We plan to discuss the safe and secure storage of the device and pods in their homes. Additionally, we will clearly label the SREC packaging so that participants are aware the SREC is used "for investigational purposes only."

Clinical study staff are the first line of staff to monitor and assess AEs and UPs. These will be assessed at each study visit after week 2. They will be recorded in REDCap responses to short surveys and in written responses to interview questions. Staff will notify [name] about these events during weekly supervision, but [name] will also receive emails as Adverse Event Reports are submitted to the REDCap database. Plans will be developed to manage and monitor AEs and UPs. SAEs will be immediately reported to the medical monitor, [name]. [name] will address these with the participant to ensure that the participant is linked with appropriate follow-up medical care. In our REDCap database, we will have a programmed report for AEs and UPs that can be run as needed for review to ensure that our understanding of adverse events and problems is always up to date.

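### Table 2 marks adverse events in every week from 3 to 14, but the AE query is scheduled at only six visits and not at all in weeks 14 to 18; these places need reconciling

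*Combined protocol and SAP*

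**What the plan says.** Table 2 in Section 6.3 has a row beginning "Adverse Events (e.g., throat irritation, nausea". It is marked in each of weeks 3 to 14 and blank at weeks 1, 2 and 18.

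Section 11.0 says that AEs are identified by querying participants after treatment starts at week 2 "through end of treatment (i.e., at weeks 3, 4, 6, 8, 11, and 14) using a standardized AE Patient Query Form". Later in the same section, on AEs and unexpected problems: "These will be assessed at each study visit after week 2". Section 6.2 ties the AE form, the nicotine-toxicity check and the lung-injury (EVALI) check to study visits as well.

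For weeks without a visit, Table 1 lists only the daily use reports. Section 6.3, item B describes them: "Daily surveys ask about the number of cigarettes smoked and the number of SREC or other e-cigarette episodes on the previous day". It adds a question on whether a pod was finished, and names no symptom item.

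On visit spacing, the design overview in Section 6.0 has participants "complete daily reports of product use along with bi-weekly check-ins through the end of the 12-week trial", while the description of weeks 5 to 13 in the same section says: "Participants will return to the study office every 2 to 3 weeks to return pods, receive a new supply, and complete CO assessments".

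At week 18, Table 1 lists "Brief follow-up about cigarette and ENDS use over past month". Section 11.0 defines an AE as "any untoward medical or psychological event experienced by a patient during or as a result of his/her participation in the study", and Section 6.0 gives the total duration per participant as 18 weeks.

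**The concern.** Staff cannot follow both the table and the text. A coordinator working from Table 2 would expect AE data in weeks 5, 7, 9, 10, 12 and 13; one working from Section 11.0 would collect none. The completeness checks in Sections 8.0 and 10.0 would then have no agreed denominator for AE data.

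Timing matters because several safety steps depend on an event becoming known. The automatic notification and the safety monitor's review follow submission of an AE report. The 72-hour and 5-business-day reporting clocks run from detection or discovery, so they do not count the time between onset and the next query. There are no formal safety stopping rules, which leaves the DSMB reliant on what the AE data show.

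After week 14 the question is one of coverage. The AE definition extends over participation, but structured collection stops four weeks before participation ends, even though a survey contact already exists at week 18.

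**Working it through.** **Inputs**
- AE marks: weeks 3 to 14, 12 columns (Table 2).
- Scheduled queries: weeks 3, 4, 6, 8, 11 and 14 (Section 11.0). These are exactly the in-person visits after week 2 in Table 1, so the plan's list of six is reproduced.
- Start of product use: week 2. End of treatment: week 14. End of participation: week 18.

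**Marked weeks without a query.** Removing the six visit weeks from weeks 3 to 14 leaves 5, 7, 9, 10, 12 and 13: 12 − 6 = 6 of 12.

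**Gaps between queries, counted from week 2**

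| Interval (weeks) | 2–3 | 3–4 | 4–6 | 6–8 | 8–11 | 11–14 |
|---|---|---|---|---|---|---|
| Gap g | 1 | 1 | 2 | 2 | 3 | 3 |

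The gaps sum to T = 12 weeks. The last two exceed two weeks.

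**Delay from onset to the next scheduled query.** Assume that onset is uniform over weeks 2 to 14, all visits are attended, and there is no contact in between. An onset falls in gap g with probability g/T and then waits g/2 on average, so the mean delay is Σg² / (2T).
- As scheduled: (1 + 1 + 4 + 4 + 9 + 9) / (2 × 12) = 28/24 = 1.17 weeks, or 8.2 days. Maximum 3 weeks.
- Weekly, as Table 2 marks: 12 gaps of 1 week give 12/24 = 0.5 week, or 3.5 days. Maximum 1 week.
- Share waiting more than 1 week: Σmax(0, g − 1)/T = (0 + 0 + 1 + 1 + 2 + 2)/12 = 6/12 = 50%.
- Share waiting more than 2 weeks: (1 + 1)/12 = 16.7%.

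**Early against late.** In weeks 2 to 4 the mean delay is (1 + 1)/(2 × 2) = 0.5 week. In weeks 8 to 14 it is (9 + 9)/(2 × 6) = 1.5 weeks.

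**After treatment.** Week 14 to week 18 is 4 weeks. Measured from first supply, that is 4 of 18 − 2 = 16 weeks, or 25%, with no scheduled AE query.

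**Week 18 content.** Table 2 marks the respiratory questionnaire (SGRQ) at weeks 1, 14 and 18. Table 1 and the week 18 description in Section 6.0 do not list it, and Section 9.0, Aim 2 places respiratory symptoms at baseline and end only. The mark cannot be relied on as it stands.

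**The case against.** The strongest reply is that the text is consistent and only one table row is loose. Sections 6.2 and 11.0 repeatedly tie AE and symptom checks to visits. Table 2 also marks non-visit weeks for intentions to use e-cigarettes, which the daily survey as described does not ask about. Correcting the row would remove that contradiction without any new data collection. This stands, and the plan does not settle which was meant. On the other side, Table 2 leaves non-visit weeks blank for breath CO, vital signs, withdrawal and craving, so it does distinguish visit-only measures. The documents nowhere say that the AE marks mean recording events whenever they are reported.

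Four stronger readings are tempting, and the documents do not support them.

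- A reader might infer that symptoms between visits are lost. An attended visit delays the scheduled query by at most three weeks. AEs learned of through other contacts are also documented and followed up; the calls named in Sections 6.2 and 11.0 are examples, not a closed list.
- A reader might infer that protection begins only with an AE form. Participants are taught the warning symptoms, pod supply is capped, daily reports are used to monitor nicotine exposure, and dispensing can be stopped because of use as well as AEs.
- A reader might infer that reported AE counts are too low. The plan gives no figure for recall loss, so only possible under-counting can be claimed. Both arms receive all assessments, so the schedule itself creates no difference in AE collection between them.
- A reader might turn the three-week gaps into an amount of product used between checks. Table 1 gives a two-week supply at week 8 and no stated amount at week 11, so the documents do not support such a figure.

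Uniform onset is also unfavourable to the plan for nicotine-related events. Section 6.2 expects any rise in exposure early, when visits are weekly. The second EMA wave asks about feeling sick and throat irritation, but only between weeks 3 and 4, and its data stay on the phone until the visit.

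**Conclusion.** The concern holds as a reconciliation point with an inexpensive improvement attached. The table and the text disagree for 6 of 12 weeks, the bi-weekly wording does not fit two three-week gaps, and four weeks of participation have no scheduled AE query. The cost of visit-only querying is a mean delay of 1.17 weeks instead of 0.5, with a maximum of 3 instead of 1. These figures rest on even onset, full attendance and no spontaneous report. A missed visit would lengthen the delay; early onset or a report between visits would shorten it.

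Brief events between late visits, and events in weeks 14 to 18, may be under-counted. The other safeguards reduce this but do not replace a scheduled question. Return of the device and remaining pods at week 14 makes later product-related events less likely, but does not change the AE definition. Even if the SGRQ is given at week 18, it is not a general AE or hospitalisation query, and the plan does not link it to AE notification.

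**What to change.** 1. Reconcile the AE row of Table 2, the query schedule in Section 11.0, the bi-weekly wording (Sections 1.0, 3.0 and 6.0) and the week 18 content, including the SGRQ mark.
2. Add a question on adverse events and hospital visits to the existing week 18 web or phone survey, and mark week 18 in the AE row.
3. State what the weekly marks mean. If weekly collection is intended, add one symptom item in each of weeks 5, 7, 9, 10, 12 and 13 to the existing REDCap survey, with a positive answer triggering the existing AE notification. If it is not intended, correct the table to the six visits.

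The cost is some survey programming, a wording change through the IRB, a little participant time, and some additional minor AE reports for the safety monitor to review.
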